8.4 Assessment of Adverse Event Causality

The investigator's assessment of causality must be provided for all AEs (serious and nonserious); the investigator must record the causal relationship on the eCRF, and report such an assessment in accordance with the SAE reporting requirements, if applicable. An investigator's causality assessment is the determination of whether there exists a reasonable possibility that the IP caused or contributed to an AE; generally, the facts (evidence) or arguments to suggest a causal relationship should be provided. The relationship of each AE to study medication will be assessed using the categories in Table 4.

Table 4. Adverse Event Causality

Causality Category	Description
Related	An adverse event that follows a reasonable temporal sequence from administration of a drug (including the course after withdrawal of the drug), or for which possible involvement of the drug cannot be ruled out, although factors other than the drug, such as underlying diseases, complications, concomitant drugs and concurrent treatments, may also be responsible.
Not related	An adverse event that does not follow a reasonable temporal sequence from administration of a drug and/or that can reasonably be explained by other factors, such as underlying diseases, complications, concomitant drugs and concurrent treatments.

If the investigator does not know whether or not the IP caused the event, then the event will be handled as "related to IP" for reporting purposes, as defined by the sponsor. If the investigator cannot determine the etiology of the event but determines that IP did not cause the event, this should be clearly documented on the eCRF and SAE Report Form if applicable.

8.5 Assessment of Adverse Event Severity

The investigator may use the CTCAE Version 5.0 to assist in the determination of severity and clinical significance. The following represents CTCAE grading of AE severity:

- **Grade 1 / Mild:** asymptomatic or mild symptoms or clinical or diagnostic observations only or intervention not indicated
- **Grade 2 / Moderate:** minimal, local or non-invasive intervention indicated or limiting age-appropriate instrumental activities of daily living (ADLs). Instrumental ADLs refer to preparing meals, shopping for groceries or clothes, using the telephone, managing money etc

- **Grade 3 / Severe or Medically Significant But Not Immediately Life-threatening:** hospitalization or prolongation of hospitalization indicated or disabling or limiting self-care ADLs. Self-care ADLs refer to bathing, dressing and undressing, feeding self, using the toilet, taking medications and not bedridden
- **Grade 4 / Life Threatening Consequences:** urgent intervention indicated.
- **Grade 5 / Death Related to AE**

AEs not listed by the CTCAE will be graded as follows:

- **Grade 1 / Mild:** discomfort noticed but no disruption of normal daily activity
- **Grade 2 / Moderate:** discomfort sufficient to reduce or affect daily activity
- **Grade 3 / Severe:** inability to work or perform normal daily activity
- **Grade 4 / Life Threatening:** represents an immediate threat to life
- **Grade 5 / Death**

8.6 Adverse Event of Special Interest

An AESI is an AE (serious or nonserious) of scientific and medical concern specific to the Sponsor's product or program, for which ongoing monitoring and immediate notification by the Investigator to the Sponsor is required. Such events may require further investigation in order to characterize and understand them. These events should be marked "AESI" in the EDC. Adverse events of special interest may be added or removed during a study by protocol clarification note or amendment.

AESIs for this study:

- Conjunctivitis
- Keratitis
- Anaphylaxis (definition below)
- AE of injection site reaction lasting >24 hours (guidance below)
- AST/ALT elevated >5X ULN
- Parasitic and opportunistic infections
- Pregnancy
- Symptomatic overdose (i.e. overdose of study drug resulting in an adverse event)

Conjunctivitis and keratitis have been subjects of interest in the dupilumab experience. (Akinlade 2019) reported that in the combined dupilumab experience in atopic dermatitis patients (n = 1047) there were a total of 90 (8.6%) patients reporting at least 1 AE of “conjunctivitis” while those patients in the placebo group (n = 517) reported 11 (2.1%) such events. Conjunctivitis AEs were mostly mild to moderate in severity with severe events reported in ≤ 0.5% of the dupilumab combined group vs. ≤ 0.3% of the placebo group. Two patients in the dupilumab group permanently discontinued study drug treatment due to a conjunctivitis event. Onset typically occurred during Weeks 4 to 8 and events became less common with long-term treatment. Conjunctivitis was more common in those patients with severe AD at baseline, those with a prior history of conjunctivitis and those with higher baseline levels of TARC and IgE. Pooled dupilumab data suggested that conjunctivitis incidence may decrease with higher trough concentrations of dupilumab.

This pattern was not observed in dupilumab studies in other indications including asthma and CRSwNP.

Due to the dupilumab experience in atopic dermatitis, ophthalmic adverse events of “conjunctivitis” and “keratitis” will be considered AEs of Special Interest (AESI) and may be evaluated by an ophthalmologist if deemed advisable by the Investigator or Sponsor. The appropriate treatment should be rendered until resolution.

Other. In addition to conjunctivitis and keratitis, the following AE's will also be categorized as AESI's: anaphylaxis, injection site reactions lasting longer than 24 hours, AST/ALT elevated >5X ULN, parasitic and opportunistic infections, pregnancy, and symptomatic overdose.

Anaphylaxis will be defined by a collection of symptoms described by Sampson et al. 2006 and provided below:

Anaphylaxis is highly likely when any one of the following 3 criteria are fulfilled:

1. Acute onset of an illness (minutes to several hours) with involvement of the skin, mucosal tissue, or both (eg, generalized hives, pruritus or flushing, swollen lips-tongue-uvula) AND AT LEAST ONE OF THE FOLLOWING:
 - a. Respiratory compromise (eg, dyspnea, wheeze-bronchospasm, stridor, reduced Peak Expiratory Flow (PEF), hypoxemia)
 - b. Reduced blood pressure (BP) or associated symptoms of end-organ dysfunction (eg, hypotonia [collapse], syncope, incontinence)
2. Two or more of the following that occur rapidly after exposure to a likely allergen for that patient (minutes to several hours):
 - a. Involvement of the skin-mucosal tissue (eg, generalized hives, itch-flush, swollen lips-tongue-uvula)
 - b. Respiratory compromise (eg, dyspnea, wheeze-bronchospasm, stridor, reduced PEF, hypoxemia)
 - c. Reduced BP or associated symptoms (eg, hypotonia [collapse], syncope, incontinence)

d. Persistent gastrointestinal symptoms (eg, crampy abdominal pain, vomiting)

3. Reduced BP after exposure to known allergen for that patient (minutes to several hours); systolic BP of less than 90 mm Hg or greater than 30% decrease from that person's baseline.

Injection Site Reaction. Assessment of the previous injection site will be done prior to dosing and again following the new injection prior to release of the patient from the clinic. An assessment tool is provided in Appendix D as an aid in the assessment of common symptoms of injection site reactions. The use of the assessment tool is encouraged but the Investigator may use their own judgement and description of symptoms in the assessment of injection sites following administration of IMP. An Injection Site Reaction should be reported as an Adverse Event if the Investigator judges the reaction as clinically significant. As a general guidance, a parameter grade of less than 2 is generally considered not clinically significant but the Investigator should use their judgement in the reporting of AEs. If the AE of Injection Site Reaction lasts longer than 24 hours, it will be considered an AESI.

Parasitic or Opportunistic Infections should be considered. Questions concerning whether or not an infection is considered an opportunistic infection may be discussed with the Medical Monitor. The Investigator may also refer to Winthrop et al. 2015 for guidance in reporting of opportunistic infections.

8.7 Mandatory Early Termination

Using CTCAE Version 5.0, patients who develop any related grade 2 or higher cardiovascular, respiratory or hematologic (example eosinophilia) TEAE or any related grade 3 or higher TEAE involving other organ systems must be discontinued from further study drug treatment and monitored until resolution or stabilization.

8.8 Serious Adverse Event Reporting

Serious AEs must be reported to the Sponsor or designee within 24 hours of knowledge of the event, if the SAE is fatal or life-threatening, notification to sponsor/CRO must be made immediately, irrespective of the extent of available event information.

All SAEs must be reported immediately (within 24 hours of discovery) by email to Parexel with copy to the Sponsor:

SAE Reporting email: [contact]

Copy to Sponsor: [contact]

Parexel Safety SAE Reporting [contact]

Parexel Safety Reporting Help Line: [contact]

24/7 Emergency Sponsor contact: [contact]

The initial report should include all information known at the time of the report (additional information can be reported as discovered). Do not delay the initial reporting in order to obtain resolution or follow-up information.

Suzhou Connect Biopharmaceuticals, Ltd

Protocol CBP-201-WW003

Investigational Drug: CBP-201

21 December 2021

The site will report SAE(s) by completing a SAE Report Form, which is provided by sponsor/CRO. In general, this will include a description of the AE in sufficient detail to allow for a complete medical assessment of the case and independent determination of possible causality. Any information relevant to the event, such as concomitant medications and illnesses must be provided. SAE Report Form will include the following information, as available:

- Patient ID number
- Country where event occurred
- Event Information
- List of relevant test results and laboratory data
- Any other relevant history
- Whether the study drug treatment was discontinued
- Investigator's assessment of causality

The CRO Medical Monitor or CRO designee / Sponsor designee may contact the Investigator to request additional information regarding the event or to confirm information. All SAEs will be entered on the AE case report form. The same nomenclature should be used on both the SAE report form and the AE case report form. The Investigator is responsible for the complete and timely reporting of all SAEs to the Sponsor (or designee), reporting pertinent follow-up information on the SAE, and notifying the appropriate IRB/IEC of the occurrence of and details surrounding the event in accordance with local regulations. In the event there is a question as to whether the AE is serious, the event should be reported.

Any SAE brought to the attention of the Investigator at any time after the end of the study for the patient and considered by him/her to be caused by the study medication with a reasonable possibility, should be reported to the monitoring team or sponsor/designee within 24 hours.

8.8.1 Suspected Unexpected Serious Adverse Reactions

Serious AEs and suspected unexpected serious adverse reactions (SUSARs) are not treated differently until an SAE is determined to be a SUSAR. The Investigator will report all SAEs to the SPONSOR within agreed timelines.

An AE is "unexpected" only if its nature and severity are not consistent with the information provided by the Sponsor about the medicinal product. In the case of a product with a marketing authorization, this information is found in the summary of product characteristics; in the case of any other investigational medicinal product, it is found in the Investigator's Brochure relating to the trial in question. There is limited clinical experience with CBP-201 in patients with rhinosinusitis with nasal polyps and asthma. Because dupilumab is a marketed product in the same class that binds to the same target (IL4Ralpha), SAEs not currently reflective of safety presented in the dupilumab package insert, from the Investigator's Brochure, or SAEs not consistent with the medical history of the patient will be considered as SUSARs.

A SUSAR that is fatal or life-threatening must be reported to the IRB/EC, the US Food and Drug Administration (FDA), and/or other competent authorities within 7 days after the Sponsor becomes aware of the event. The Investigator is responsible for notifying the IRB/EC and the Sponsor is responsible for notifying the competent regulatory authorities. Any additional information must be reported within 8 days of sending the first report.

A SUSAR that is not fatal or life-threatening must be reported to IRB/EC, FDA, and/or other competent authorities as soon as possible (within 15 days) after the Sponsor becomes aware of the event. The Investigator is responsible for reporting to the IRB/EC and the Sponsor is responsible for notifying the competent regulatory authorities.

In addition, SUSARs will be reported to any IRBs/ECs and Principal Investigators as required in the local legislation. Reporting will be to the European Medicines Agency and EU member states via Eudravigilance.

Periodic and annual reporting will be performed per country-specific guidelines.

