1.3 Effects in Humans

CONNECT has completed 3 Phase 1 clinical studies and is in progress with 3 Phase 2 clinical studies and 1 Phase 2/3 clinical study in humans to date that are described in this document. The first study was a single ascending dose Phase 1a study to assess the safety, tolerability, pharmacokinetics (PK), and pharmacodynamics (PD) of CBP-201 in healthy volunteers as the first-in-human study in Australia. A second similar single ascending dose study has been completed in healthy volunteers in China. The third study was a multiple ascending dose Phase 1b study to assess safety, tolerability, PK, and PD of CBP-201 in adult patients with atopic dermatitis. A Phase 2 clinical study in patients with atopic dermatitis in the US, Australia, New Zealand, China, and the European Union (EU) has recently completed dosing and is in the reporting phase. A Phase 2 study in patients with asthma is on-going in

Suzhou Connect Biopharmaceuticals, Ltd

Protocol CBP-201-WW003

Investigational Drug: CBP-201

21 December 2021

the US with additional planned sites in China and the EU, Ukraine and South Korea. A Phase 2/3 study in atopic dermatitis patients is also in progress in China.

To date there has been one un-related death from myocardial infarction and 7 additional unrelated serious adverse events (chest pain, rib fracture secondary to auto accident, cholelithiasis, headache, nausea, vomiting and pneumonia) occurring in the recently completed double-blind Phase 2 trial of CBP-201 in patients with moderate-to-severe atopic dermatitis. Most reported treatment-emergent adverse events (TEAEs) to date have been mild to moderate in severity. No clinically relevant trends in clinical safety laboratory data or vital sign data have been observed across doses or over time up to 1 to 4 months of treatment.

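### Protocol section 8.8.1 gives two inconsistent tests for which SAEs are SUSARs, and the second is not tied to the causality assessment

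*Protocol*

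**What the plan says.** Protocol section 8.8.1 opens with a restrictive definition. An adverse event is unexpected only if "its nature and severity are not consistent with the information provided by the Sponsor about the medicinal product". For a licensed product the reference is its authorised labelling. Of unlicensed products the section says: "in the case of any other investigational medicinal product, it is found in the Investigator's Brochure relating to the trial in question". CBP-201 is unlicensed, so the Brochure is the only reference under this test.

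Later in the same paragraph, on the ground that dupilumab is marketed and binds the same target, a second sentence covers "SAEs not currently reflective of safety presented in the dupilumab package insert", names the Brochure next in the same list, and adds that "SAEs not consistent with the medical history of the patient will be considered as SUSARs".

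SUSAR status starts the reporting clocks in the same section: 7 days if the event is fatal or life-threatening, otherwise 15 days. Section 8.4 requires the investigator to judge causality for every adverse event, using the two categories of Table 4, and treats an unknown cause as related for reporting purposes. Section 8.8.1 does not refer to that judgement.

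**The concern.** The two sentences cannot both be applied. The first admits one reference document. The second adds another company's label and the patient's own history. It also states no condition that the event be related to study drug. Its list is unclear as well: only a comma separates the dupilumab insert from the Brochure, so it does not say whether an SAE must be absent from either document or from both.

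This decides which events go to regulators and ethics committees on an expedited timetable. Too wide a rule fills that channel with unrelated or already known events. Too narrow a rule delays external notice of a reaction that is new for CBP-201.

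**Working it through.** The plan gives no figure to reproduce, so the check is logical. Describe each SAE by four yes/no facts taken from the two sentences and section 8.4:

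- R: assessed as related
- P: reflected in the dupilumab insert
- B: consistent with the CBP-201 Brochure
- H: consistent with the patient's medical history

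This gives 2 × 2 × 2 × 2 = 16 combinations. Compare three rules:

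1. **Reference rule** (the definition of unexpected, plus the suspected reaction in the term itself): R and not B. Count: 1 × 1 × 2 × 2 = 4.
2. **Second sentence, absence from either document is enough**: not P, or not B, or not H. Only P, B and H all being true escapes, once for each value of R. Count: 16 − 2 = 14.
3. **Second sentence, absence from both documents is needed**: (not P and not B), or not H. For each value of R there are 4 combinations with H false, plus 1 with H true and the event in neither document. Count: 2 × (4 + 1) = 10.

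| Rule | Flagged | Of these: unrelated | Of these: related, already in Brochure | Missed against reference |
|---|---|---|---|---|
| Reference | 4 | 0 | 0 | – |
| Either document | 14 | 7 | 3 | 0 |
| Both documents | 10 | 5 | 2 | 1 |

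The rows reconcile. For the either-document reading, 4 + 7 + 3 = 14, so 10 are extra. For the both-documents reading, (4 − 1) + 5 + 2 = 10, so 7 are extra. The one missed combination is an SAE that is related, absent from the Brochure, present in the dupilumab insert, and consistent with the patient's history.

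Every case flagged under the both-documents reading is also flagged under the either-document reading. The two therefore agree in 12 of 16 combinations and differ in 14 − 10 = 4: those where the event fits the history and is listed in exactly one document.

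Protocol section 1.3 offers an illustration. It reports 1 death and 7 other SAEs from the atopic dermatitis trial, 8 in all, each called unrelated. With relatedness required, 0 of 8 are SUSARs. Under the second sentence relatedness is not asked, so even "rib fracture secondary to auto accident" would be one if it did not fit that patient's history. No histories are given, so how many of the 8 would qualify is unknown.

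**The case against.** The strongest reply is that the sentence should not be read alone. The term being applied is a suspected adverse reaction, which already implies a causal link. Section 8.8.1 speaks of an SAE being determined to be a SUSAR, and section 8.4 ties the causality judgement to SAE reporting. A competent safety group might well apply relatedness without being told. This stands in part: a reader might infer that the protocol drops causality, and it does not. What is missing is any link from the classification sentence to that judgement, and the documents do not show how the sponsor would apply it.

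A reader might also say that the section defines SUSAR twice. It does not. The first sentence defines only *unexpected*, one element of a SUSAR, and the second keeps the Brochure and adds to it. The conflict is between an expectedness definition and a classification rule.

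A third inference is that new CBP-201 reactions would be withheld because dupilumab already has them. That follows only from the both-documents reading, in 1 of 16 combinations, and only by setting aside the restrictive definition earlier in the same paragraph. Nor would the sponsor be unaware of the event. Section 8.8 sends every SAE to the sponsor or its designee within 24 hours, section 8.6 requires immediate notification of events such as conjunctivitis, keratitis and anaphylaxis, and a DSMB reviews safety. The exposure is confined to expedited reporting outside the sponsor.

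**Conclusion.** The contradiction is real and should be corrected. The main consequence is over-reporting, which arises under both readings of the second sentence: 10 or 7 combinations beyond the reference rule, of which 7 or 5 are unrelated SAEs. Under-reporting is a narrower, conditional risk.

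This rests on literal application of the text, and on a reference rule that takes relatedness from the term SUSAR and the Brochure from the protocol's own definition. The 16 combinations are not equally likely, so the counts must not be read as proportions of events. The number of events affected would depend on the Brochure, the dupilumab insert and patient histories, none of which the documents supply. The eight earlier SAEs come from another indication and show how the rule works, not how often it would misfire.

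No endpoint or efficacy analysis is affected. SAP section 4.15 records early termination, which limits the practical gain within this trial. The point is not moot: the analysis now focuses on safety, and section 8.8 keeps SAEs attributed to study drug reportable after a patient's participation ends.

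**What to change.** Replace the two sentences with one rule: a SUSAR is an SAE assessed as related under section 8.4 and unexpected against the CBP-201 Investigator's Brochure. Keep the protocol's own *nature and severity* wording unless the sponsor decides deliberately to change it. State that the dupilumab insert and the patient's medical history may inform medical review but do not determine expectedness.

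The cost is one paragraph in an amendment, or in a clarification if that suits a trial that is closing. The small downside is that some class-type reactions not yet in the CBP-201 Brochure will need expedited reports.

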8.9 Pregnancy Reporting

For the purposes of this study, pregnancy of any female patient will be considered an AESI and should be reported within 24 hours to the medical monitor and Sponsor on the Pregnancy Form. The patient will be asked to provide information on the outcome of the pregnancy, including premature termination (elective abortion). Spontaneous miscarriage and congenital abnormalities will be reported as an SAE and an SAE form should be submitted. Pregnancy itself is not an SAE. Female patients becoming pregnant during the study and after randomization must be immediately withdrawn from study drug treatment and followed to resolution, which includes birth or termination of the pregnancy. Every attempt should be made to follow the pregnancy to completion. If possible, births will be followed by the Investigator for 8 weeks for observation of possible congenital abnormalities. Pregnancies of a male patient's partner will not be considered an AE and the male patient should not be withdrawn from the study. If a male patient's partner becomes pregnant during this time period (from first dose until 8 weeks after the last dose), the Investigator will inform the Sponsor, and the IRB or EC, as appropriate, as well as providing the appropriate medical follow-up if agreed to by the partner.

